5.3.4 Investigational Imaging Agent Administration: N/A

5.4 For Phase 1 Protocols Only: Definition of Dose-Limiting Toxicity (DLT): N/A

5.5 General Concomitant Medication and Supportive Care Guidelines

Because there is a potential for interaction of ivabradine with other concomitantly administered drugs through the cytochrome P450 system, the case report form must capture the concurrent use of all other drugs, over-the-counter medications, or alternative therapies. The Overall PI should be alerted if the participant is taking any agent known to affect or with the potential to affect selected CYP450 isoenzymes. [Appendix C](#) presents guidelines for identifying medications/substances that could potentially interact with the study agent(s).

5.6 Criteria for Taking a Participant Off Protocol Therapy

Patients will receive ivabradine or placebo for a total of 6 weeks. Treatment may continue for 6 weeks or until one of the following criteria applies:

- Intercurrent illness that prevents further administration of treatment
- Unacceptable adverse event(s)
- Participant demonstrates an inability or unwillingness to comply with the oral medication regimen and/or procedure/documentation requirements
- Participant decides to withdraw from the protocol therapy
- General or specific changes in the participant's condition render the participant unacceptable for further treatment in the judgment of the treating investigator

Participants will be removed from the protocol therapy when any of these criteria apply. The reason for removal from protocol therapy, and the date the participant was removed, must be

documented in the case report form (CRF). Alternative care options will be discussed with the participant.

An ODQ Treatment Ended/Off Study Form will be filled out when a participant is removed from protocol therapy. This form can be found on the DF/HCC website at <http://www.dfhcc.harvard.edu/research/clinical-research-support/document-library-forms-sops-etc/>.

In the event of unusual or life-threatening complications, treating investigators must immediately notify the Overall PI, *[name]* at [contact] [name].

5.7 Duration of Follow Up

Participants will be followed till the end of the study protocol. Participants removed from protocol therapy for unacceptable adverse event(s) will be followed until resolution or stabilization of the adverse event.

5.8 Criteria for Taking a Participant Off Study

Participants will be removed from study when any of the following criteria apply:

- Lost to follow-up
- Withdrawal of consent for data submission
- Death

The reason for taking a participant off study, and the date the participant was removed, must be documented in the case report form (CRF).

For Centralized Subject Registrations, the research team submits a completed Off Treatment/Off Study form to ODQ when a participant comes off study. This form can be found on the ODQ website or obtained from the ODQ registration staff.

For Decentralized Subject Registrations, the research team updates the relevant Off Treatment/Off Study information in OnCore.

6. DOSING DELAYS/DOSE MODIFICATIONS

All patients will be started on ivabradine 5 mg po twice daily or placebo. Dose modifications will be made at the 2 week visit as indicated in the following table(s).

Heart Rate	Dose Adjustment
> 60 bpm	Increase dose to 7.5 mg p.o. twice daily
50-60 bpm	Maintain dose at 5 mg p.o. twice daily
< 50 bpm or signs and symptoms of bradycardia	Decrease dose to 2.5 mg p.o. twice daily

If the patient continues to have symptomatic bradycardia or HR < 50 on 2.5 mg twice daily,

ivabradine will be discontinued. Placebo will be used in a similar manner. Patients will be maintained on the best tolerated dose for a total of 4 weeks.

If symptomatic bradycardia occurs on ivabradine 7.5 mg or 5 mg twice a day at any point in the study, without objective hemodynamic compromise (SBP > 80 mm Hg), the medication can be resumed at a lower dose (2.5 mg reduction) after a 24 hour drug-free interval (i.e. 1 missed dose). If symptomatic bradycardia persists despite dose reduction, then the study drug will be further reduced by 2.5 mg or discontinued as per the discretion of the investigator. A maximum of 2 dose reductions would be allowed for patients on 7.5 mg twice daily and 1 dose reduction for those on 5 mg twice daily. Patients requiring dose reduction will not have a subsequent dose escalation at any point during the study.

Any patients with symptoms of bradycardia after drug titration will be brought in for an additional clinical evaluation and EKG.

Overdosage of ivabradine may lead to severe and prolonged bradycardia. In the event of bradycardia with poor hemodynamic tolerance, the drug should be withdrawn. Supportive treatment, including intravenous fluids, atropine, intravenous beta-stimulating agents (isoproterenol) or temporary pacing may be considered.

7. ADVERSE EVENTS: LIST AND REPORTING REQUIREMENTS

Adverse event (AE) monitoring and reporting is a routine part of every clinical trial. The following list of reported and/or potential AEs (Section 7.1) and the characteristics of an observed AE (Section 7.2) will determine whether the event requires expedited reporting **in addition** to routine reporting.

7.1 For CTEP protocols only: Comprehensive Adverse Events and Potential Risks List(s) (CAEPRs): N/A

7.2 For CTEP protocols only: Adverse Event Characteristics: N/A

7.3 For CTEP protocols only: Expedited Adverse Event Reporting: N/A

7.4 For CTEP protocols only: Routine Adverse Event Reporting: N/A

7.5 For CTEP protocols only: Secondary Malignancy: N/A

7.6 For CTEP protocols only: Second Malignancy: N/A

7.7 Expected Toxicities

7.7.1 Adverse Events List(s)

7.7.1.1 Adverse Event List(s) for Ivabradine

- a) Fetal toxicity
- b) Atrial fibrillation
- c) Bradycardia
- d) Conduction disturbances including heart block and sinus arrest
- e) Ventricular arrhythmias including torsades de pointes, ventricular fibrillation, and ventricular tachycardia
- f) Hypotension
- g) Syncope
- h) Hypertension
- i) Phosphenes (luminous phenomenon)
- j) Angioedema
- k) Erythema
- l) Rash
- m) Pruritis
- n) Urticaria
- o) Vertigo
- p) Diplopia
- q) Visual disturbance

7.7.1.2 Adverse Event List(s) for Other Agent(s): N/A

7.8 Adverse Event Characteristics

- **CTCAE term (AE description) and grade:** The descriptions and grading scales found in the revised NCI Common Terminology Criteria for Adverse Events (CTCAE) version 4.0 will be utilized for AE reporting. All appropriate treatment areas should have access to a copy of the CTCAE version 4.0. A copy of the CTCAE version 4.0 can be downloaded from the CTEP web site http://ctep.cancer.gov/protocolDevelopment/electronic_applications/ctc.htm.
- **For expedited reporting purposes only:**
 - AEs for the agent(s) that are listed above should be reported only if the adverse event varies in nature, intensity or frequency from the expected toxicity information which is provided.
 - Other AEs for the protocol that do not require expedited reporting are outlined in the next section (Expedited Adverse Event Reporting) under the sub-heading of Protocol-Specific Expedited Adverse Event Reporting Exclusions.
- **Attribution** of the AE:
 - Definite – The AE *is clearly related* to the study treatment.
 - Probable – The AE *is likely related* to the study treatment.
 - Possible – The AE *may be related* to the study treatment.
 - Unlikely – The AE *is doubtfully related* to the study treatment.
 - Unrelated – The AE *is clearly NOT related* to the study treatment.

7.9 Expedited Adverse Event Reporting

7.9.1 Investigators **must** report to the Overall PI any serious adverse event (SAE) that occurs after the initial dose of study treatment, during treatment, or within 30 days of the last dose of treatment on the local institutional SAE form. Serious criteria includes: death, hospitalization, event that results in disability, life-threatening event, congenital anomaly, or any event determined to be medically significant by the investigator.

7.9.2 N/A

7.9.3 DF/HCC Expedited Reporting Guidelines

Investigative sites within DF/HCC will report AEs directly to the DFCI Office for Human Research Studies (OHRS) per the DFCI IRB reporting policy.

7.9.4 N/A

7.10 Expedited Reporting to the Food and Drug Administration (FDA): N/A

7.11 Expedited Reporting to the NIH Office of Biotechnology Activities (OBA): N/A

7.12 Expedited Reporting to the Institutional Biosafety Committee (IBC): N/A

7.13 Expedited Reporting to Hospital Risk Management

Participating investigators will report to their local Risk Management office any participant safety reports or sentinel events that require reporting according to institutional policy.

7.14 Routine Adverse Event Reporting

All Adverse Events **must** be reported in routine study data submissions to the Overall PI on the toxicity case report forms. **AEs reported through expedited processes (e.g., reported to the IRB, FDA, etc.) must also be reported in routine study data submissions.**

The Overall PI must report all pregnancies and pregnancies occurring in the partner of a patient participating in the study or potential infant exposure through lactation within 10 calendar days of PI's awareness to Amgen. Amgen will contact the investigator/study site and request the site attempt to obtain authorization from the pregnant or breast feeding woman to provide Amgen with pertinent information regarding the pregnancy and birth outcome or health of the breastfed infant.

8. PHARMACEUTICAL INFORMATION

A list of the adverse events and potential risks associated with the investigational or other agents administered in this study can be found in Section 7.7.

8.1 Ivabradine

[figure not shown]
8.1.1 Description

Ivabradine is a hyperpolarization-activated cyclic nucleotide gated channel blocker that reduces the spontaneous pacemaker activity of the cardiac sinus node by selectively inhibiting the I_f current, resulting in heart rate reduction with no effect on ventricular repolarization and no effects on myocardial contractility.

The chemical name for ivabradine is 3-(3-{{(7S)-3,4-Dimethoxybicyclo[4.2.0]octa-1,3,5-trien-7 yl)methyl} methyl amino} propyl)-1,3,4,5-tetrahydro-7,8-dimethoxy-2H-3-benzazepin-2-one, hydrochloride. The molecular formula is C₂₇H₃₆N₂O₅, HCl, and the molecular weight (free base + HCl) is 505.1 (468.6 + 36.5).

Ivabradine is extensively metabolized in the liver and intestines by CYP3A4-mediated oxidation. The major metabolite is the N-desmethylated derivative (S 18982), which is equipotent to ivabradine and circulates at concentrations approximately 40% that of ivabradine. The N-desmethylated derivative is also metabolized by CYP3A4. Ivabradine plasma levels decline with a distribution half-life of 2 hours and an effective half-life of approximately 6 hours. The total clearance of ivabradine is 24 L/h, and renal clearance is approximately 4.2 L/h, with ~ 4% of an oral dose excreted unchanged in urine. The excretion of metabolites occurs to a similar extent via feces and urine.

The effects of coadministered drugs (CYP3A4 inhibitors, substrates, inducers, and other concomitantly administered drugs) on the pharmacokinetics of Corlanor were studied in several single- and multiple dose studies. Pharmacokinetic measures indicating the magnitude of these interactions are presented in the Figure below:

8.1.2 Form

Ivabradine is manufactured by Amgen under the trade Corlanor. It is supplied as:
 Corlanor 5 mg: salmon-colored, oval-shaped, film-coated tablet, scored on both edges, debossed with “5” on one face and bisected on the other face. The tablet is scored and can be divided into equal halves to provide a 2.5 mg dose.
 Corlanor 7.5 mg: salmon-colored, triangular-shaped, film-coated tablet debossed with “7.5” on one face and plain on the other face.

8.1.3 Storage and Stability

Store at 25°C (77°F); excursions permitted to 15° - 30°C (59° - 86°F).

8.1.4 Compatibility

N/A

8.1.5 Handling

There are no special considerations for the handling of ivabradine.

8.1.6 Availability

Ivabradine, which is commercially available, will be provided free of charge for this

study by Amgen. The study drug will be sent by Amgen to the principal investigator, [name], and will be stored and dispensed by the Investigational Pharmacy at Brigham and Women's Hospital. Matching placebo tablets will also be manufactured and stored by the Investigational Drug Pharmacy at Brigham and Women's Hospital.

8.1.7 Preparation

After randomization, ivabradine or matching placebo tablets will be supplied by the Investigational Drug Pharmacy at Brigham and Women's Hospital.

Active medication will be blinded using over-encapsulation in an empty gelatin capsule by the Investigational Drug Pharmacy at Brigham and Women's Hospital. The matching placebo will be a capsule filled with microcrystalline cellulose also prepared by the Investigational Drug Pharmacy at Brigham and Women's Hospital.

Both the patient and investigators will remain blinded to study drug assignment throughout the duration of the study.

8.1.8 Administration:

Medication will be taken P.O. twice daily with food. Medication will be taken outpatient. Pills should be swallowed whole.

8.1.9 Ordering

Ivabradine will be provided by Amgen prior to study initiation. Placebo will be manufactured by the Investigational Drug Pharmacy. Both ivabradine and placebo will be stored and dispensed by the Investigational Drug Pharmacy at Brigham and Women's Hospital.

8.1.10 Accountability

The investigator, or a responsible party designated by the investigator, should maintain a careful record of the inventory and disposition of the agent using the NCI Drug Accountability Record Form (DARF) or another comparable drug accountability form. (See the NCI Investigator's Handbook for Procedures for Drug Accountability and Storage.)

8.1.11 Destruction and Return

Unused and expired supplies of ivabradine will be returned to Amgen at the end of the study.

8.2 IND Agent #2: N/A

8.3 Other Agent #1: N/A

8.4 Other Agent #2: N/A

9. BIOMARKER, CORRELATIVE, AND SPECIAL STUDIES

9.1 Biomarker Studies: N/A

9.2 For IDE Protocols Only: Investigational Device Information: N/A

9.3 Laboratory Correlative Studies: N/A

9.4 Other Agent #2: N/A

10. STUDY CALENDAR

Baseline evaluations/tests are to be conducted within 1 week prior to start of protocol therapy. In the event that the participant's condition is deteriorating, laboratory evaluations should be repeated within 48 hours prior to initiation of therapy.

2 week study evaluations and drug up-titration should be administered within ± 3 days of the protocol-specified date, unless otherwise noted.

Week 6 study evaluations/tests should be conducted within ± 7 days of the protocol-specified date and should be completed prior to termination of study drug.

	Screening visit	Baseline	Week 2	Week 6
Agents:		Ivabradine vs. placebo	Ivabradine or placebo dose titration	Study End
Informed consent	X			
Demographics	X			
Medical history	X		X	X
Physical exam		X	X	X
Concurrent Meds	X	X	X	X
Vital signs	X	X	X	X
Height		X		X
Weight		X		X
Serum chemistry ^a	X			
EKG (as indicated)	X	X	X	X
B-HCG		X ^b		X ^b
Exercise stress test		X		X
24-hr ambulatory Holter monitor		X		X
SF-36 QOL questionnaire		X		X
Sophisticated autonomic function testing ^c		X		X
Adverse event evaluation		X-----X		
a: Review of SGOT [AST], SGPT [ALT], creatinine obtained within the last 12 months. b: Urine pregnancy test (women of childbearing potential). c: For subset of patients randomized to receive autonomic function testing				

11. MEASUREMENT OF EFFECT

11.1 Antitumor Effect- Solid Tumors: N/A

11.2 Antitumor Effect- Hematologic Tumors: N/A

11.3 Other Response Parameters

Primary end point:

1. Change in HR from baseline to 6 weeks with ivabradine vs. placebo.¹⁷

Secondary end point:

1. Change in exercise duration from baseline to 6 weeks with ivabradine vs. placebo.²³

Exploratory end points:

1. Change in markers of additional cardiac autonomic function: respiratory sinus arrhythmia amplitude, Valsalva ratio, heart rate variability, cardiovagal CASS and adrenergic CASS from baseline to 6 weeks.¹⁹
2. Change in patient reported quality of life (as assessed using then SF 36 questionnaire) from baseline to 6 weeks with ivabradine compared to placebo.²⁴

12. DATA REPORTING / REGULATORY REQUIREMENTS

Adverse event lists, guidelines, and instructions for AE reporting can be found in Section 7.0 (Adverse Events: List and Reporting Requirements).

12.1 Data Reporting

12.1.1 Method

The Office of Data Quality (ODQ) will collect, manage, and perform quality checks on the data for this study.

12.1.2 Responsibility for Data Submission

Investigative sites within DF/HCC or DF/PCC are responsible for submitting data and/or data forms to the Office of Data Quality according to the schedule set by the DF/HCC SOPs.

12.1.3 Confidentiality Protections

Data will be obtained from a complete history, physical examination, symptom limited exercise stress test, 24 hour ambulatory Holter monitor, cardiac autonomic testing, and a self-reported health related quality of life questionnaire (SF-36) before and after the 6

week treatment period. Data will also be collected from the 14-day safety visit. The data will be shared with investigators/personnel involved in the study and will be retained for at least 5 years after completion of the study. The data source files will be kept in a locked room in the cardiovascular offices at Brigham and Women's Hospital. The data will be stored in a de-identified manner in an encrypted Partners computer.

The identifiable information will not be reused or disclosed except as consistent with this protocol and signed HIPAA Authorization for Research.

12.2 Data Safety Monitoring

The DF/HCC Data and Safety Monitoring Board (DSMB) will review and monitor study progress, toxicity, safety and other data from this study. The board is chaired by a medical oncologist from outside of DF/HCC and has external and internal representation. Information that raises any questions about participant safety or protocol performance will be addressed by the Overall PI, statistician and study team. Should any major concerns arise, the DSMB will offer recommendations regarding whether or not to suspend the study.

The DSMB will meet twice a year to review accrual, toxicity, response and reporting information. Information to be provided to the DSMB may include: participant accrual; treatment regimen information; adverse events and serious adverse events reported by category; summary of any deaths on study; audit results; and a summary provided by the study team. Other information (e.g. scans, laboratory values) will be provided upon request.

12.3 Multicenter Guidelines: N/A

12.4 Collaborative Agreements Language: N/A

13. STATISTICAL CONSIDERATIONS

This is a randomized double-blind, placebo-controlled study evaluating the effect of ivabradine on resting heart rate and exercise capacity in survivors of lymphoma with mediastinal involvement who were treated with mediastinal/mantle RT.

Survivors of mediastinal RT have increased cardiovascular morbidity and mortality. We have previously shown that thoracic RT is associated with cardiac autonomic dysfunction, as measured by elevated resting HR and abnormal HRR after exercise.¹² Furthermore, we were the first to report that these abnormalities are associated with impaired exercise tolerance and increased mortality (for HRR only) among 263 HL survivors treated with RT.¹² Furthermore, HL survivors treated with RT had a blunted BP response to exercise.¹² Ivabradine is a drug that lowers HR without significantly impacting BP. We hypothesize that ivabradine will lower HR in HL survivors treated with RT. We further hypothesize that this reduction in HR will lead to increased exercise capacity, improved sympatho-vagal balance, and improved health related quality of life in these patients.

The study will enroll adult survivors of lymphoma with mediastinal involvement (including both

Non-Hodgkin's Lymphoma and Hodgkin's Lymphoma) who have been treated with mediastinal/mantle radiation at least 5 years prior to enrollment and have a resting heart rate ≥ 80 bpm. The detailed eligibility criteria are outlined in sections 3.1 and 3.2 above.

13.1 Study Design/Endpoints

Primary End point:

The primary objective of this study is to investigate whether ivabradine lowers resting HR, compared to placebo, in survivors of lymphoma with mediastinal involvement who were treated with mediastinal/mantle radiation and have a resting HR ≥ 80 bpm.

Secondary End-point:

The secondary objective of this study is to evaluate whether ivabradine improves exercise duration, compared to placebo, in survivors of lymphoma with mediastinal involvement who were treated with mediastinal/mantle radiation and have a resting HR ≥ 80 bpm.

Exploratory End-points:

- 1) To evaluate whether ivabradine improves additional markers of cardiac sympatho-vagal balance, compared to placebo, in survivors of lymphoma with mediastinal involvement who were treated with mediastinal/mantle radiation and have a resting HR ≥ 80 bpm.
 - 2) To evaluate whether ivabradine improves health related quality of life, compared to placebo, in survivors of lymphoma with mediastinal involvement who were treated with mediastinal/mantle radiation and have a resting HR ≥ 80 bpm.
- The patients will be accrued on a continuous basis from the out-patient survivorship, cardio-oncology, and radiation oncology clinics at DFCI, Massachusetts General Hospital, Brigham and Women's Hospital, and Boston Children's Hospital till target accrual is completed. Eligible patients from sites other than the Brigham will be referred to the Brigham for all study procedures.
 - There are no explicit early stopping rules for this study. However, the data will be reviewed periodically by the DFCI DSMB and the study will be terminated if the DSMB deems it necessary to do so.
 - The target sample size for this study is 54 patients. We plan to enroll a total of 60 patients to account for screen failure, resting HR < 80 at baseline visit, withdrawals, or loss to follow up. Based on our clinical volume, we plan to recruit 2-3 patients per month over a cumulative accrual period of 24-36 months. Each patient will be followed for the 6 week duration of the study. There is no long-term follow-up planned in this study.
 - We hypothesize that ivabradine will lower resting HR, compared to placebo, in survivors of lymphoma with mediastinal involvement who were treated with mediastinal/mantle radiation

and have a resting HR \geq 80 bpm. We further hypothesize that this reduction in HR will be associated with increased exercise duration in these patients.

- In the Ivabradine and chronic outcomes in heart failure (SHIFT) trial, the net reduction in heart rate with ivabradine was 10.9 (95% CI 10.4-11.4) bpm, with a standard deviation of 10.5 bpm. Thus, with a sample size of 27 patients in each group, we will have 95% power to detect this net reduction in heart rate assuming a probability of making a type I error of 0.05.¹² To allow for incomplete primary end point data due to withdrawals or loss to follow up, we will aim to recruit 30 patients in each group.
- With a sample size of 27 subjects in each group, we will have 90% power to detect a clinically meaningful improvement of 34% in exercise duration on treadmill testing assuming a probability of making a type I error of 0.05, an improvement in the placebo group of 12%, and a standard deviation of 24%.
- All patients will first be stratified into two groups according to pre-randomization treatment with beta-blocking agents. Patients within each beta-blocker group will then undergo four way randomization using permuted blocks, dividing the two strata into four groups each: ivabradine with sophisticated autonomic testing, placebo with sophisticated autonomic testing, ivabradine with no sophisticated autonomic testing, placebo with no sophisticated autonomic testing. These four groups will be created in a 1:1:1:1 ratio. Randomization will be performed by the ODQ at Dana Farber Cancer Institute.
- If patients are randomized into the sophisticated autonomic testing group and are not able to complete sophisticated autonomic function testing for any reason, but are willing to continue taking the study medication (ivabradine or placebo), they will be encouraged to continue taking part in all other study protocols for the duration of the study: twice daily ivabradine or placebo, history and physical exam, EKG, SF-36 questionnaire, exercise treadmill test, and 24 hour ambulatory holter monitoring.

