2. BACKGROUND

2.1 Study Disease(s)

Thoracic radiation therapy (RT) is associated with an increased risk of cardiovascular morbidity and mortality.^{1,2} In particular significant delayed cardiotoxicity has been observed among long-term survivors of Hodgkin lymphoma (HL) treated with mantle/mediastinal radiation.^{3,4} These patients also frequently report exercise intolerance. Elevated resting heart rate and abnormal heart rate recovery following exercise are established markers of cardiac autonomic dysfunction⁵ and are strongly associated with cardiovascular morbidity and mortality in the general population

⁶⁻¹¹ as well as in survivors of Hodgkin lymphoma treated with mediastinal RT.¹²

Heart rate and rhythm are largely regulated by the autonomic nervous system. Parasympathetic influence is mediated via acetylcholine release by the vagus nerve and sympathetic influences are mediated via the secretion of epinephrine and norepinephrine. Acetylcholine reduces heart rate by increasing the potassium conductance of pacemaker cells in the sino-atrial node¹³ and inhibiting the hyperpolarization activated I_f channel to delay slow diastolic depolarization.¹⁴ Conversely, sympathetic activation increases intracellular calcium¹⁵ and activates the I_f channel¹⁶ to accelerate slow diastolic depolarization and increase heart rate. We have previously shown that thoracic RT is associated with autonomic dysfunction, as measured by elevated resting heart rate and abnormal heart rate recovery.¹² Furthermore, we were the first to report that these abnormalities are associated with impaired exercise tolerance among 263 Hodgkin lymphoma survivors treated with RT. Exercise duration was significantly reduced among RT patients with an elevated resting heart rate (9.2 ± 2.9 versus 10.7 ± 3.1 minutes, $p < 0.0001$) and those with abnormal heart rate recovery (8.3 ± 3.1 versus 10.6 ± 2.9 minutes, $p < 0.0001$).¹² We hypothesize that this is related to depressed parasympathetic stimulation secondary to RT-induced injury to the vagus nerve.

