13.6 Analysis of Secondary Endpoints

The secondary end-point of this study is the change in exercise duration with ivabradine, compared to placebo, in survivors of lymphoma with mediastinal involvement who were treated with mediastinal/mantle radiation and have a resting HR \geq 80 bpm.

We will calculate the change in exercise duration (from exercise treadmill stress tests) from baseline to 6 weeks for each patient in the study (n=60). An ANCOVA model (for normally distributed data) adjusting for the stratification factors (beta blocking agents [Yes, No], autonomic function testing [Yes, No]) or Quade test adjusting for the stratification factors (beta blocking agents [Yes, No], autonomic function testing [Yes, No]) (for non-normally distributed data) will be implemented to compare the change in exercise duration with ivabradine versus placebo.

We will then repeat the analysis with change in resting HR as an additional independent variable to assess whether change in resting HR affects exercise duration. A p value < 0.05 using a two-sided test will be considered statistically significant.

Exploratory end-points of this study are:

- 1) Change in additional markers of cardiac sympatho-vagal balance with ivabradine, compared to placebo, in survivors of lymphoma with mediastinal involvement who were treated with mediastinal/mantle radiation and have a resting HR \geq 80 bpm.

Since this is an exploratory end-point and due to cost constraints, it will only be conducted in half the patients enrolled in the trial (n=30) and no power calculation has been made. The cardiovagal composite autonomic severity score (CASS) and adrenergic CASS will be calculated at baseline and at 6 weeks (as described in Section 5.3.3) for each patient in this substudy. The change in CASS and adrenergic CASS will then be assessed for each patient. Quade test adjusting for the stratification factors (beta blocking agents [Yes, No], autonomic function testing [Yes, No]) (for ordinal data) will be implemented to compare the change in CASS and adrenergic CASS in patients treated with ivabradine versus placebo. A p value < 0.05 using a two-sided test will be considered statistically significant.

- 2) Change in health related quality of life with with ivabradine, compared to placebo, in survivors of lymphoma with mediastinal involvement who were treated with

mediastinal/mantle radiation and have a resting HR \geq 80 bpm.

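### Exercise duration is powered on percent change, but Section 13.6 names no analysis scale and does not adjust for baseline duration

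*Combined protocol and SAP*

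**What the plan says.** Section 13.1 gives the power statement for the secondary endpoint. With 27 per group, "we will have 90% power to detect a clinically meaningful improvement of 34% in exercise duration on treadmill testing", under a type I error of 0.05, "an improvement in the placebo group of 12%, and a standard deviation of 24" per cent. No source is given for the 34%, the 12% or the 24%.

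Section 13.6 describes the analysis: "We will calculate the change in exercise duration (from exercise treadmill stress tests) from baseline to 6 weeks for each patient". The groups are compared by ANCOVA, or by a Quade test if the data are not normal. Either is adjusted for beta-blocker use and for assignment to autonomic function testing, and baseline duration is not listed. The criterion is "A p value < 0.05 using a two-sided test will be considered statistically significant". Section 11.3 defines the endpoint in the same unscaled way.

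The only treadmill durations in the documents are in Section 2.1, in minutes. For irradiated survivors with and without elevated resting heart rate they are "9.2 ± 2.9 versus 10.7 ± 3.1 minutes". The same sentence gives 8.3 versus 10.6 minutes for abnormal and normal heart rate recovery.

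**The concern.** The power is set on one scale and the analysis is described on none. A reader of Section 13.6 alone could compute a difference in minutes, a percent change or a ratio, and each fits the text. Three things follow.

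- The 90% is tied to percent change. If minutes are analysed, nothing in the documents shows what the power is.
- The scale could be chosen after the data are seen, on the only secondary endpoint.
- Leaving out baseline duration gives up precision that is available at no cost. Treadmill time varies widely between patients (SD about 3 minutes in Section 2.1), and Section 5.3.3 already requires a baseline test in everyone.

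The wording of the effect adds to this. Thirty-four per cent is presented as the improvement to be detected, which reads like a treatment effect. The calculation works only if 34% is the gain in the ivabradine arm and the contrast is 34 − 12 = 22 points.

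**Working it through.** **Inputs.** From Section 13.1: 27 per arm, 34% versus 12%, SD 24%, alpha 0.05. From 13.6: two-sided test. From 2.1: 9.2 (SD 2.9) and 10.7 minutes; 8.3 and 10.6 minutes.

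**1. The plan's own figure.** Standardised effect = (34 − 12)/24 = 0.917. Noncentrality = 0.917 × √(27/2) = 3.37 on 52 degrees of freedom. Two-sided power is 91.1% (noncentral t), and 90% power needs 26.01 per arm, which rounds up to 27. The stated 90% reproduces. Taking 34% as the net effect would give 99.9%, so 22 points is the intended contrast.

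**2. Moving to minutes, first route.** On a base of 9.2 minutes, 22% is 0.22 × 9.2 = 2.02 minutes. If the SD of change is simply 24% of 9.2 = 2.21 minutes, power stays at 91.1%. Suppose instead that baseline is normal (9.2, SD 2.9) and percent change is independent of it. Then

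Var(change) = (9.2² + 2.9²) × 0.24² + 2.9² × m²,

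where m is the arm's mean gain. This gives an SD of 2.34 minutes for placebo (m = 0.12) and 2.52 for ivabradine (m = 0.34). Simulated power is then:

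| Analysis | Power |
|---|---|
| Percent change | 91% |
| Minutes, no baseline covariate | 86% |
| Minutes, baseline as covariate | 88% |
| Log ratio, log baseline as covariate | 90% |

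Independence is an assumption. With a negative correlation between baseline and percent change, as regression to the mean would produce, power in minutes without the covariate is about 89–90% at −0.2 and 92–94% at −0.4 to −0.5.

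**3. Moving to minutes, second route.** Assume an SD of 2.9 minutes at both visits and a baseline to week-6 correlation r. The SD of change is 2.9 × √(2(1 − r)). With baseline as a covariate, the residual SD is 2.9 × √(1 − r²). For a difference of 2.02 minutes:

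| r | SD of change | Power without baseline | Residual SD | Power with baseline |
|---|---|---|---|---|
| 0.5 | 2.90 | 71% | 2.51 | 83% |
| 0.6 | 2.59 | 80% | 2.32 | 88% |
| 0.7 | 2.25 | 90% | 2.07 | 94% |
| 0.8 | 1.83 | 98% | 1.74 | 99% |

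Simulation of the first two rows gave 69% to 81% and 81% to 88%.

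**4. Smaller effects, on the percent scale with SD 24%.** The gap for elevated resting heart rate is 10.7 − 9.2 = 1.5 minutes, and 1.5/9.2 = 16.3%. Power is 68.8%. The gap for abnormal heart rate recovery is 10.6 − 8.3 = 2.3 minutes, and 2.3/8.3 = 27.7%. Power is 98.6%.

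**The case against.** The strongest reply is that nothing here is miscalculated. The power figure reproduces, Section 13.6 never says minutes, and reading 13.1 and 13.6 together a sponsor could say that percent change was meant all along. The endpoint is secondary in a Phase II/pilot study, and 27 per group is separately justified on heart rate. All of that stands. It limits the point to an unspecified scale and an omitted covariate.

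Two stronger conclusions are tempting, and the documents do not support them.

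- A reader might infer that true power is 86% and that the plan should say so. That figure depends on percent change being independent of baseline, which the documents neither state nor allow one to check. Other equally admissible assumptions put power in minutes at or above 90%.
- A reader might infer that the target is impossible, because a net 2.0 minutes exceeds the 1.5-minute gap and 9.2 × 1.34 = 12.3 minutes exceeds 10.7. The gap is a cross-sectional difference between survivors, not a bound on a treatment effect. The 12.3 minutes includes the assumed 12% placebo gain, which the 10.7 does not. The heart-rate-recovery gap, 2.3 minutes, is larger than the target, although recovery is not an eligibility criterion. Section 5.3.3 also lists reaching 85% of age-predicted maximal heart rate among the reasons to end the test, and Section 2.3 expects about 10 bpm lower heart rate during exercise. Duration could therefore lengthen beyond any untreated gap. Plausibility of the effect is in any case a separate question from the scale of the test.

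The covariate is also not guaranteed to help in minutes. If change in minutes happens to be unrelated to baseline, it gains nothing and costs one degree of freedom.

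**Conclusion.** The point holds as a gap in specification. Section 13.1 fixes power on percent change, while Section 13.6 names no scale and omits baseline duration. The 90% is correct for the inputs given and should not be replaced by a lower figure.

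Its size depends on what is assumed. On the percent or log-ratio scale, power is about 90–91%. In minutes without baseline it is about 86–94% for correlations of 0 to −0.5 between baseline and percent change, or about 70–98% for baseline to week-6 correlations of 0.5 to 0.8. Adding baseline is worth about 2 points under the first route at correlation 0. Under the second it is worth about 12 points at r = 0.5 and 8 at r = 0.6. These ranges assume that the Section 2.1 cohort resembles the trial population. That cohort is Hodgkin survivors only, and Section 2.1 states no heart rate cut-off for elevated, so the match is approximate.

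This is a free improvement. It does not put the trial size or the primary analysis in question.

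**What to change.** In Section 13.6:

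- Name the scale used for power. One suitable choice is log(week-6 duration / baseline duration), with log baseline duration as a covariate, back-transformed to a percent difference.
- Keep both stratification factors, beta-blocker use and autonomic testing, in the model.
- Carry baseline duration into the Quade fallback, and use the same scale in the repeat analysis that adds change in heart rate. Align Section 11.3.

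In Section 13.1:

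- State the effect as a net 22 points (34% versus 12%) and give the source of the 34%, 12% and 24%.
- Optionally, add that power is about 69% for a net 16%, the cross-sectional gap for elevated resting heart rate in Section 2.1, labelled as a benchmark and not a ceiling.
- Do not restate power as 86%.

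The cost is wording, with no extra patients, visits or measurements. One degree of freedom goes to the covariate. A ratio is slightly less familiar than minutes, and its size differs from the points difference: 1.34/1.12 = 1.196, so 22 points corresponds to a back-transformed difference of roughly 20%. A summary in minutes can be reported alongside as description.
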